size based on the observed differences in outcomes such as HRQoL (SF-36 and prostate cancer index, PCI) and cost of PCa care across groups. The primary outcome is HRQoL as measured by the SF-36 and PCI sub-scales. A change of 5 to 9 points on PCI is clinically meaningful [272]. Similarly, a difference of 7 points or more on the SF subscales is considered clinically meaningful [272, 275, 301]. Based on our prior research and that of Litwin et al [253, 272], the standard deviations for the PCI and SF-36 scales in samples of men with PCa mostly range from 8 to 14; hence standardized differences (SDs) of $7/14=0.5$ to $7/8=0.87$ will be clinically relevant. The power calculations for Aims 2-4 assume availability of 720 participants who are eligible for randomization into one of the two intervention groups. We assume a conservative intra-class correlation of 0.3 and 4 follow-up measures per subject. The sample size is adjusted to accommodate a 10% missing or dropout rate by 24 months based on rates over a similar period of time in previous studies [272, 275, 301]. We assume 80% power and two-sided level of significance of $\alpha = 0.05$. We have 80% power to detect a 1.2 point difference in PCI or SF-36 sub-scale. Within treatment type, the sample size is reduced to 60 per intervention arm. We have 80% power to detect a 3.0 point difference in sub-scale with 60 patients in each arm. Thus, we will have adequate power to detect differences between treatment groups [302]. Power for identifying utility based profiles and outcomes: We analyzed the levels of power for differences in outcomes between profiles defined by latent classes of attributes-specific utilities with a conservative allocation of subjects to each profile (25 in one vs. 10 in other profile) and less conservative allocation (35 in one profile vs. 35 in other profile) using a logistic model based comparison for a binary outcome (e.g. recovery of baseline HRQoL) with a 2-sided alpha of .0125 (Holms adjustment profiles). In the first allocation, the group difference of 0.56 yields 80% power; for the second allocation an effect size of 0.42 corresponds to power of 90. Thus, with our anticipated effect size of 0.51, we will have adequate power with $n=60$ in each group. (Adjusting for patient characteristics may reduce the effect sizes of the differences between profiles.)

Key inclusion criteria

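### The stated 80% power for 1.2 points overall and 3.0 points within treatment type is tied to no SD or contrast; as a four-visit mean it holds only near SD 8 of the plan's 8–14 range

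*Combined protocol and SAP*

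**What the plan says.** The sample-size text (Characteristics of the Study Population, Accrual) names HRQoL on the SF-36 and PCI sub-scales as primary and says its calculations serve Aims 2–4. Its inputs are 720 participants, 80% power, two-sided 0.05, and:

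- "the standard deviations for the PCI and SF-36 scales in samples of men with PCa mostly range from 8 to 14"
- "We assume a conservative intra-class correlation of 0.3 and 4 follow-up measures per subject"
- an allowance for 10% loss over the 24 months

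The results are "We have 80% power to detect a 1.2 point difference in PCI or SF-36 sub-scale" and, by treatment type, "We have 80% power to detect a 3.0 point difference in sub-scale with 60 patients in each arm". The conclusion is "Thus, we will have adequate power to detect differences between treatment groups [302", where the number is a literature citation.

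Its benchmarks are "A change of 5 to 9 points on PCI is clinically meaningful" and "a difference of 7 points or more on the SF subscales is considered clinically meaningful".

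The Analysis Plan for Specific Aim 3 uses a mixed model with random intercepts and slopes. At each time point of interest it compares the arms on change from baseline, and it also stratifies by type of treatment.

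**The concern.** A detectable difference scales directly with the SD, so a range of 8 to 14 cannot give a single figure. The contrast matters as much: a mean over four visits has a much smaller variance than a change from baseline at one visit when the correlation is 0.3. The text fixes neither, yet concludes without qualification that power is adequate.

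What is at stake is how the within-type comparisons are read. With 60 per arm, someone who trusts the 3.0-point figure could take a null result as evidence against a difference that the comparison had little power to show.

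**Working it through.** **Inputs.** SD 8 to 14, ICC 0.3, four follow-up measures, two-sided 0.05, 360 and 60 per arm, 10% loss (all from Accrual and Target population). It is not stated outright whether 360 and 60 are before or after loss, so both are used: 360 or 360 × 0.9 = 324, and 60 or 60 × 0.9 = 54.

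**Formulas.** With n per arm and variance factor v (variance of the per-patient summary divided by SD²):

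- detectable difference = (1.960 + 0.842) × SD × √(2v/n)
- power for d = Φ( d / (SD × √(2v/n)) − 1.960 )

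**Reproducing the plan's figures.** For the unadjusted four-visit mean, v = (1 + 3 × 0.3)/4 = 0.475. At SD 8:

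- n = 324: 2.802 × 8 × √(0.95/324) = 1.21; n = 360: 1.15
- n = 54: 2.802 × 8 × √(0.95/54) = 2.97; n = 60: 2.82

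So 1.2 and 3.0 can be obtained from the stated inputs.

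**Across the plan's own SD range (same contrast).** Power for 1.2 or 3.0 points:

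| SD | 1.2 points (n = 324 / 360) | 3.0 points (n = 54 / 60) |
|---|---|---|
| 8 | 79% / 83% | 81% / 85% |
| 11 | 52% / 57% | 54% / 58% |
| 14 | 35% / 39% | 37% / 40% |

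The largest SD that keeps 80% is 7.9 to 8.5. Adjusting the four-visit mean for baseline (assumed correlation 0.3, v = 0.475 − 0.09 = 0.385) raises that only to 8.8–9.5.

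**Another route to the same figures.** With v = (1 − 0.3)/4 = 0.175, SD 14 and n = 360 / 60, the detectable differences are 1.22 / 3.00. That factor leaves out between-subject variance, so it does not describe a between-arm difference in means. It does show that the derivation cannot be inferred from the result.

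**Aim 3 contrast.** The correlation r between baseline and a follow-up visit is not given; 0.3 (the plan's ICC extended to baseline) and 0.7 are assumptions. For one visit, simple change has v = 2(1 − r), and baseline-adjusted analysis has v = 1 − r². Detectable differences, each cell running from n = 360 to 324 or from 60 to 54:

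| Contrast | v | Overall, SD 8 | Overall, SD 14 | Within type, SD 8 | Within type, SD 14 |
|---|---|---|---|---|---|
| Four-visit mean | 0.475 | 1.15–1.21 | 2.01–2.12 | 2.82–2.97 | 4.94–5.20 |
| Simple change, r = 0.3 | 1.40 | 1.98–2.08 | 3.46–3.65 | 4.84–5.10 | 8.47–8.93 |
| Baseline-adjusted, r = 0.3 | 0.91 | 1.59–1.68 | 2.79–2.94 | 3.90–4.11 | 6.83–7.20 |
| Simple change, r = 0.7 | 0.60 | 1.29–1.36 | 2.26–2.39 | 3.17–3.34 | 5.55–5.85 |
| Baseline-adjusted, r = 0.7 | 0.51 | 1.19–1.26 | 2.09–2.20 | 2.92–3.08 | 5.11–5.39 |

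Of the four change contrasts, only the last reaches 1.2 and 3.0, at SD 8 and n = 360 / 60 (1.19 / 2.92).

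**Against the plan's benchmarks, at SD 14.**

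- Overall, 5 points: above 99% (four-visit mean); 97–98% (simple change, r = 0.3).
- Within type, 5 points: 77–81% (four-visit mean); simple change 35–38% (r = 0.3) to 67–71% (r = 0.7).
- Within type, 7 points: 97–98% (four-visit mean); simple change 59–64% (r = 0.3) to 92–94% (r = 0.7).

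**The case against.** - **The source of the figures is unknown.** A reader might infer that the authors picked SD 8 as the favourable end, or slipped in the arithmetic. The documents support neither. Several constructions give about 1.2 and 3.0, including the SD 14 route above. Calling an ICC of 0.3 conservative also suits a change or slope better than a mean, for which a low ICC is favourable. This stands.
- **The Aim 3 shortfall is conditional.** The plan estimates change from a fitted model with random slopes, which pools information across visits, and its 0.3 is given alongside the follow-up measures, not baseline. A reader might conclude that the Aim 3 contrast cannot reach the stated figures; at r = 0.7, baseline-adjusted, SD 8 and no loss from 360 / 60, it does. With time linear over 0, 3, 6, 12 and 24 months, ICC 0.3 and no random-slope variance, SD 8 and n = 324 / 54 give 1.86 / 4.56 at 24 months, still short. At 12 months they give 0.93 / 2.28, but linearity then makes the 24-month difference twice the 12-month one. The condition stands; it does not rescue the figures at r = 0.3 or at the upper SDs.
- **Loss is probably already covered.** The Subject recruitment text expects 800 baseline assessments to secure 720, and 800 × 0.9 = 720, which suggests 720 and 60 are net of loss. That favours the better end of each range and changes little.
- **Adequate power survives on one reading.** At SD 14 and 60 per arm the four-visit mean detects 4.94 points, just under the lowest benchmark. This is true, but the Aim 3 text does not describe that contrast.

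**Conclusion.** The point holds as a reporting fault with a measurable size. The two stated differences carry about 80% power only near SD 8 when read as a between-arm four-visit mean; elsewhere in the plan's SD range, power for them falls to 52–58% (SD 11) and 35–40% (SD 14). For change from baseline at one visit they are missed at SD 8 if the baseline correlation is 0.3, and are reached only with a much higher correlation and SD near 8.

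A reader might go on to infer that the trial is too small. The figures do not support that: at SD 14 the overall comparison keeps at least 97% power for 5 points. What is unsupported is the unqualified claim of adequate power within treatment type.

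The result rests on normal approximations, equal correlations between visits, and an assumed baseline correlation of 0.3 to 0.7. All figures use 0.05. The Analysis Plan also calls for a Bonferroni correction without a number of tests; any such correction would lower power further, and no figure is put on it here.

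**What to change.** In the Accrual sample-size paragraph:

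1. Replace the single figures with detectable differences over SD 8–14, naming the contrast. For the four-visit mean these are 1.15–2.1 points overall and 2.8–5.2 within type.
2. Give the matching figures for the Aim 3 change-from-baseline contrast, stating the assumed baseline correlation and showing a range such as 0.3–0.7. For simple change at one visit that is 2.0–3.6 overall and 4.8–8.9 within type at 0.3, and 1.3–2.4 and 3.2–5.8 at 0.7.
3. Qualify the statement of adequate power for the within-type comparisons with those figures.

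This costs about a paragraph of text. The sample size, data collection and tests stay as they are; the only loss is that the stated figures become less favourable.

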2.2.7 Phase 2 2.2.7.1 Specific Aim 1: To develop values markers, we first will assess individual level utilities, followed by latent profile analysis based on these individual level utilities as described below. Individual utilities for attributes of treatment (conjoint task): The conjoint task requires PCa patients to make choices between hypothetical treatment options based on the attributes identified in the Phase 1 focus groups. Each participant will be asked to express his preference for attributes of various PCa treatments based on choice sets presented, varying in the attribute levels of the various treatment choices ascertained in Phase 1. Precisely which attributes will be used will be refined based on piloting the conjoint task with a small number of participants (n=20). The balancing or trade-off of treatment features will be captured in the patient-specific utilities or part-worths associated with the attribute levels in the study. The discrete choice conjoint analysis is based on a mixed effects logistic model with a pair of fixed and random effects defined for each attribute, which is treated as a covariate. We assume two attributes, x_1 and x_2 with binary discrete choice response variable Y . The corresponding mixed effects logistic model for the mean of Y ($=E(Y | x_1, x_2)$) is: Estimation of β_1, β_2 and is based on an empirical Bayes approach using maximum likelihood estimates (MLE) of β_1 and β_2 . Under this approach, we assume that β_1, β_2 and have a multivariate normal distribution with mean zero and variance-covariance Σ . MLE of β_1, β_2 and is based on marginal likelihood derived from integrating β_1, β_2 and from the likelihood. With estimates of β_1, β_2 and we obtain empirical Bayes estimates of β_1, β_2 and Σ . This estimation will be performed in SAS (Proc NLMIXED), which also will allow us to assess the sensitivity of this modeling approach to assumptions of normality of the random effects utility parameters by trying non-normal random effects distributions. Values markers (latent profiles based on individual utilities): We will carry out additional analyses of individual-level utilities to classify patients according to profiles or patterns of utilities using latent profile analysis. The profiles that are derived from the latent profile analysis will determine the value markers representing patterns of treatment attributes that the patients value. The empirical Bayes estimates of the subject-level utilities then can be used as inputs to a growth curve mixture model (i.e., Latent Profile Analysis) to obtain patterns of treatment preferences as represented by the estimated utilities from the conjoint analysis. Such patterns correspond to latent classes based on a random effects linear model with multivariate set of utilities as the continuous dependent variables [300]. This model will be implemented in Mplus Version 6.12. The number of classes will be determined using the Lo-Mendell-Rubin (LMR) adjusted likelihood ratio test. Mplus reports a bootstrapped p-value to account for departures from model assumptions, such as the multivariate normal distribution of the attribute-specific utilities. We will describe these profiles in terms of descriptive statistics of the multivariate set of attribute-set utilities.

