patients in decision (measured using CPS) using multi-nominal regression model to adjust for observed covariates. Then we will examine if these associations vary across intervention and usual care control groups. We then will repeat the model with other independent variables (decision conflict and trust). Next, we will test the association denoted by path c (direct effect of DCS, CPS, and trust on outcomes). For continuous outcomes (HRQoL, AUA-SI, MAX-PC, CES-D, SWD, and PSQ-18), we will compute area under the curve (AUC) for each measure for each patient. We will analyze AUC summaries with univariate linear models. In our main analysis we will analyze the series of functional status measures using linear mixed models that predict the outcome from time, independent variables and their interaction. We will repeat the analyses described for path c, this time by including treatment received in the models. We will test if the observed effects of DCS, CPS or trust on outcomes will be weaker after controlling for treatment. These analyses will be performed within and between groups (intervention and usual care controls). Specific Aim 3: Hypothesis: Prostate cancer patients in the intervention group undergoing conjoint analysis-value clarification exhibit improved treatment choice, satisfaction with decision, lower regrets, and improved objective and subjective outcomes. Analysis for Specific Aim 3 uses intent-to-treat approach: all randomized participants will be included regardless of whether they drop out of the intervention or study. Analysis will involve comparison of the primary outcomes between intervention and usual care control groups. Improved treatment choice is operationalized as the likelihood of low-risk PCa patients receiving active surveillance than active treatment, and will be compared between intervention and usual care control group. To allow for different trajectories of the outcome measures and to afford flexibility in making contrasts within participants over time and across participants, while simultaneously controlling for potential confounders, we propose the participant-specific or mixed effects linear model, in which the mean outcome depends on fixed covariates and random effects. The primary fixed effects will be indicators for intervention group and hospital. We will also stratify the analysis by type of treatment. The random effects represent the unobserved factors that lead to variation of the individual participants outcome. Random intercepts for each participant permit modeling of natural variation across participants at baseline. In addition, random slopes or random effects for the trajectory of each participant over time, allow for variation of each participant about a mean, overall trajectory across all participants. Although less robust to model misspecification, the mixed effects paradigm offers special flexibility in longitudinal data when exposures vary over time and when dropout and missed visits lead to unbalanced groups. The target of inference is the participant-specific response to treatment over time. At each time point of interest, we will estimate from the fitted model the difference from baseline in outcome for the treatment and control groups and test the difference between these differences. Both univariate and multivariate results will be reported in terms of Wald test, point estimates, and 95% confidence intervals. Specific Aim 4: Hypothesis 4: Prostate cancer patients whose treatment is more concordant with their values markers will experience improved subjective and objective outcomes. This specific aim s for intervention group only. We will analyze the association of the concordance between stated individual preferences and actual treatment received with objective (PCa recurrence and complications), subjective (HRQoL, psychological wellbeing, SWD, and satisfaction with care) outcomes, across treatment groups, adjusting for covariates. Association between the value markers (profiles) and measures of outcomes and personal and clinical characteristics: The value markers will be studied for their relationship with socio-demographic and clinical characteristics. We will also assess the association of value markers with outcomes. We will perform logistic regression with outcomes as the dependent variable and dummy variables for the utility-based profiles obtained earlier as independent variables. We will perform this evaluation with and without adjusting for patient attributes in the logistic model. For each case (adjusting and not adjusting for patient attributes), the evaluation of association between these profiles and outcomes will be based on a likelihood ratio test of the set of odds ratios corresponding to the dummy variables of the profiles. Additionally, we will perform a sequence of pair wise tests of comparisons of the profiles in terms of the proportion of type of treatment received based on the Holms multiple comparisons approach. This procedure is hierarchical in that it will identify the utility-based profile at the start of the process before making other comparisons, thus protecting the Type I error from additional comparisons. Specifically, Holms approach tests each pair-wise comparison in ascending order of p-values. Successively larger p-values have less rigorous alpha. The sequential Holm tests terminate after the first non-significant comparison so no subsequent comparison is significance. Concordance and its assessment: Understanding and respect for the patients preference and values is the main aspect of concordance [69, 73]. Thus a first step in concordance involves the physician extracting and understanding the patients view, followed by an agreement between the physician and patient regarding a management plan that integrates their views. There exist many definitions of concordance. For the purpose of this study, we operationalized concordance as agreement between a patients value markers and the attributes (or characteristics) of the treatment that

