
the patient receives (choice). Association of concordance between stated preference and attributes of treatment received will be studied separately for each treatment using Kappa statistics. The degree of concordance then will be used as an independent variable to test its association with outcomes. For objective/clinical outcomes (i.e., complications and PCa recurrence), we will test the hypothesis that degree of concordance is associated with PCa recurrence (measured by PSA doubling time). To evaluate the effects of concordance on biochemical recurrence of PCa, we will analyze PSA levels on the log scale over time using a mixed model approach. We also will apply survival analyses (Kaplan-Meier, logrank and Cox model) to model effects concordance of treatment and covariates on time to PSA recurrence. For subjective outcomes of urologic symptoms (AUA-SI), generic and prostate specific HRQoL, psychological well-being (CES-D, MAX-PC), satisfaction with decision and satisfaction with care, we will perform inferential analysis with t, chi-squared and non-parametric tests. Wilcoxon matched-pairs test will be used for comparisons within concordance and non-concordance groups. A concordance group will be defined as at least 75% agreement between values markers and treatment related attributes. We will perform sensitivity analysis to test robustness of results. Primary analyses will compare baseline with six and 24 months assessments, as literature suggests these are the clinically most relevant time points. Secondary analyses will compare baseline with three month and one year outcomes. Proportion returning to baseline over time will be compared using chi-squared tests, using procedures such as Bonferroni, Scheffé, and step-down Holm corrections to adjust for multiple testing. We will use loglinear regression models with psychological well being, HRQoL and satisfaction with care scores (log) as dependent variables, logistic regression with return to baseline as the dependent variable, and degree of concordance as the independent variable. For repeated measures outcomes we will use linear mixed models (Proc Mixed).

The following documents are currently attached to this item:

There are no documents attached for this item.

Deception

Does your project use deception?

No

Data confidentiality

- x Paper-based records will be kept in a secure location and only be accessible to personnel involved in the study.**

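### Does it matter that power for outcomes between preference profiles is computed at a Holm-adjusted 0.0125 when the planned outcome test is a global likelihood ratio test?

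*Combined protocol and SAP*

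**What the plan says.** In the Accrual section, the paragraph on power for utility-based profiles concerns "differences in outcomes between profiles defined by latent classes". It uses a two-profile logistic comparison of a binary outcome, such as recovery of baseline quality of life, "with a 2-sided alpha of .0125 (Holms adjustment profiles". Two allocations are considered. With 25 men against 10, "the group difference of 0.56 yields 80% power". With 35 against 35, an effect of 0.42 gives 90%. It concludes that "with our anticipated effect size of 0.51, we will have adequate power" with 60 in each group.

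The Analysis Plan for Specific Aim 4, which covers the intervention arm only, regresses outcomes on profile dummies. The evaluation "will be based on a likelihood ratio test of the set of odds ratios corresponding to the dummy variables of the profiles", with and without patient attributes. No alpha is stated. Holm appears in that section for pairwise comparisons of profiles "in terms of the proportion of type of treatment received based on the Holms multiple comparisons approach". Under Specific Aim 1, "The number of classes will be determined using the Lo-Mendell-Rubin (LMR) adjusted likelihood ratio test", so the number of profiles is not fixed in advance. Later, in the concordance analysis, "Proportion returning to baseline over time will be compared using chi-squared tests", with Holm among several permitted corrections; that analysis does not compare profiles.

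**The concern.** The test that was powered is not the test that is planned. One section assumes a pairwise comparison at 0.0125; the other plans a single global test per outcome and model at an unstated level. If the planned level were 0.05 and there were only two profiles, both sections would describe the same comparison at different thresholds. A p-value between 0.0125 and 0.05 would then be read differently depending on which section governs. The anticipated 0.51 also falls between the difference that 25 versus 10 needs at 0.0125 (0.56) and what it would need at 0.05 (about 0.46–0.49). The claim of adequate power for a small profile would seem to hang on an unresolved choice.

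**Working it through.** **Inputs.** From Accrual: two-sided 0.0125; 25 v 10 with 0.56 for 80%; 35 v 35 with 0.42 for 90%; anticipated 0.51; general two-sided level 0.05; 60 per group. Event rates and effect scale are not given. I assume differences in proportions and vary the lower rate, placed in the profile of 25.

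**1. Reproducing the plan's figures.** Power = Φ[(d − z·s0)/s1], with s0 = √[p̄(1−p̄)(1/n1+1/n2)], s1 = √[p1(1−p1)/n1 + p2(1−p2)/n2], and z = 2.498 for 0.0125.

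- 25 v 10, rates 0.13 and 0.69: p̄ = (25×0.13 + 10×0.69)/35 = 0.29; s0 = 0.1698; s1 = 0.1610; (0.56 − 2.498×0.1698)/0.1610 = 0.844; power 80.1%.
- 35 v 35, rates 0.13 and 0.55: s0 = 0.1132; s1 = 0.1015; (0.42 − 2.498×0.1132)/0.1015 = 1.35; power 91.2%.

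Lower rates of 0.12–0.16 or 0.39–0.42 match both stated figures within 2 points. The stated powers are therefore attainable and mutually consistent, though the documents' inputs alone cannot confirm them.

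**2. The anticipated 0.51 with 25 v 10 at 0.0125.** At lower rate 0.13: s0 = 0.1672; s1 = 0.1660; (0.51 − 2.498×0.1672)/0.1660 = 0.556; power 71.1%. Over the retained rates: 63–72%. Power below 80% already follows from 0.51 < 0.56.

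**3. The planned likelihood ratio test for the same 25 v 10 difference.** I assume level 0.05. Noncentrality is 2Σnᵢ[pᵢ ln(pᵢ/p̄) + (1−pᵢ) ln((1−pᵢ)/(1−p̄))], which is 8.83 at lower rate 0.13. Degrees of freedom are the number of profiles minus one. If the other profiles add no signal:

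| Profiles | df | Power at rate 0.13 | Over retained rates |
|---|---|---|---|
| 2 | 1 | 84% | 83–85% |
| 3 | 2 | 76% | 74–77% |
| 4 | 3 | 70% | 68–71% |
| 5 | 4 | 65% | 63–66% |

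If instead one profile of 10 differs by 0.51 from two, three or four profiles of 25 that share one rate, power is 80–85%, 77–84% and 74–82%. The global test may or may not reach 80%.

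**4. What 0.0125 implies.** Holm's first step is 0.05/m. Comparing all pairs of 2, 3 or 4 profiles gives m = 1, 3 or 6, hence 0.05, 0.0167 or 0.0083. With two profiles Holm leaves 0.05 unchanged. 0.05/4 = 0.0125 fits none of these families. It would fit five profiles compared with one reference, but the plan does not say so.

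**5. The conclusion at 60 per group.** Splitting 60 in the ratio 25:10 gives 60×25/35 ≈ 43 and 60×10/35 ≈ 17. At 0.51, level 0.0125, lower rate 0.13: s0 = 0.1279; s1 = 0.1272; (0.51 − 2.498×0.1279)/0.1272 = 1.50; power 93.3%. Over the retained rates: 92–94%. An equal split gives 96–98%. If 10% of the 60 are lost, both standard errors rise by √(60/54) = 1.054 to 0.1348 and 0.1341; (0.51 − 2.498×0.1348)/0.1341 = 1.29, or about 90%.

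**The case for a change.** The best argument for a change is that the two sections name different tests for the same question, that the planned test has no stated alpha, and that this leaves room to choose a threshold after seeing results. Naming one test and one alpha would cost a sentence and a recomputed paragraph.

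The mismatch, the unexplained divisor and the shortfall of 25 versus 10 at 0.0125 all stand. The claimed consequences are weaker. The conflict over p-values between 0.0125 and 0.05 requires exactly two profiles, and with two profiles a Holm correction over pairs does not lower the level at all. A divisor of four points to more comparisons, and then the global test has more degrees of freedom and may also miss 80% (step 3). So it cannot be said that 0.51 passes under one test and fails under the other. The 0.05 for the likelihood ratio test is itself an assumption, since the Analysis Plan also has a general Bonferroni rule of undefined scope.

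A significance level used to justify a sample size is also not a decision rule. The Analysis Plan sets the analysis, and its global test is a sound one for each outcome and model.

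**Conclusion.** This is a reporting inconsistency that analysts can settle sensibly by running the test in the Analysis Plan and treating the power paragraph as a planning calculation. Nothing in the design, method or sample size would change. The printed powers are attainable, and the conclusion at 60 per group holds with 92–94% power at 0.0125 and 0.51, or about 90% after 10% loss at a lower rate of 0.13. The 25 versus 10 case is underpowered at 0.0125 (63–72%), but it is the plan's deliberately conservative allocation, and its 0.56 requirement is printed beside the anticipated 0.51. A null result for a profile of about 10 men should be read with that in mind.

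These figures rest on three assumptions: effects are differences in proportions, event rates are limited to those that reproduce the plan's own numbers, and the 60 men fall into two profiles. More profiles within the same 60 would make each comparison smaller and bring it nearer the 25 versus 10 case. The number of profiles will be known only from the data, so a recomputed power figure now would replace one set of unstated assumptions with another.
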